### 360° 3D HD Video Virtual Reality

360° Video Virtual Reality (360° -VVR) refers to a three-dimensional, immersive film environment that people can interact with. Typically users interface with virtual reality via a digital head mounted display (HMD) (see Figure 5.) that immerses the user in the virtual world by blocking their vision of the outside world, so that the user can only see the three dimensional images projected on the digital display in front of their eyes.

Figure 5. Head mounted display

A key component of virtual reality is that users can guide their sensory input of the multimedia environment in a way similar to how they guide their senses in real life. The HMD typically incorporates a head tracker that is mapped to a virtual “camera” view of the three-dimensional multimedia environment so that when users turn their heads, their view of the multimedia environment shifts with them (e.g. if users look down, the camera pans down and the users see the floor). As such, unlike a 2D film, 360° - VVR is an interactive 360° viewing experience. While you can turn your head away from the experience of watching a television, with a virtual reality head mounted

## Research Proposal

---

display, if you turn your head you will only see more of the virtual world. 360°-VVR can provide powerful interactive experiences for users but until recently, the hardware necessary for virtual reality could cost tens of thousands of dollars. However in the last five years virtual reality headsets have become almost as cheap as cellphones and Google cardboard makes it even cheaper by allowing people to use their android phones as do-it-yourself VR headsets. Thus, VR headsets are no longer limited to well-funded labs but in the grasp of individuals. This technology could mean that reducing pain in hospital patients through use of VR is a practical and economical reality.

The VR treatment in this study will be administered using a Samsung Gear VR headset. The Gear VR is a new, affordable virtual reality headset, that when coupled with a Samsung Galaxy smartphone can deliver photorealistic VR footage easily to participants in a hospital setting.

### Treatment

Following the acquisition of consent and the baseline assessments, participants will be outfitted with a Samsung Gear VR headset. Before the headset is placed on the patient's head, the patient will be given the option to wear a plastic shower cap over their head for the headset straps to rest on. This was recommended by the Infection Control Preventionist at DSMC. The shower cap is not required if the patient does not desire to wear one. The research assistant will help them adjust the headset. If the participants record any discomfort, the research assistant will attempt to adjust the settings on the Samsung Gear VR. If the participant finds that regardless of the settings, they cannot watch the video comfortably, they will be thanked for their time and their participation in the study will end.

After the headset is properly calibrated, the participant will receive instructions that they are about to view VR footage of central Texas locations. At the same time, they will be told that during the task they should try to imagine that they are actually at the location experiencing the scenery first hand. Additionally, participants will be instructed not to exert their body in any capacity that may cause additional pain while experiencing the virtual environment. They will be instructed that if at any time they become uncomfortable or wish to stop using the Gear VR, they may do so at anytime. Before watching the video, patients will be outfitted with a pair of headphones. The headphone ear cushions will be covered with sanitary disposable headphone covers. The covers on each ear cushion will be disposed of in a hospital trash can after each patient is finished watching the VR video.

Participants in the enhanced film condition will view 9 minutes of VR film footage of representative Austin scenes. The 9 minutes of footage will be alternating 30 second clips of Hamilton Pool Preserve in Dripping Springs, TX, a rower on Lady Bird Lake in Austin, TX, Red Bud Isle in Austin, TX, and Zilker Botanical Gardens in Austin, TX. These locations were picked for their beauty and likeliness for participants to be immersed in and distracted by the aesthetically pleasing footage.

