## Research Proposal

---

condition ( $n = 67$ ). We anticipate we will need to recruit and consent a total of 500 participants due to the anticipated number of screen failures (due to inclusion/exclusion criteria). We hypothesize that the film VR will show greater pain reductions and increased functioning relative to both the animated VR and the waitlist condition.

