### Conditions

Participants will be randomized to the 360° 3D HD video VR film condition, animated video VR condition, or waitlist condition. Those randomized to the waitlist group will complete all study procedures except the VR exposure. After completion of the study visit, we will give those in the waitlist condition the option of experiencing the 9-minute VR video of their choosing.

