### Post-Treatment Assessments

Following the 9 minutes of VR exposure or waiting, participants in each condition will complete post-treatment assessments for 5-10 minutes. These assessments will measure pain, presence, mood, negative effects of VR, absorption, human presence, participant's prior familiarity with the locations depicted in the VR video, and their attitude toward the VR session immediately after the treatment. Nausea, dizziness, eyestrain, and head pain is being assessed in an effort to identify the incidence of this component of simulator sickness sometimes associated with VR use (Kennedy et al., 1992). Following the Post-Treatment assessments, the Follow-Up Pain Questionnaire & Present Mood Questionnaire will be administered 10 minutes following the treatment. These follow-up assessments are in place in order to track the lasting pain reduction from the VR treatments.

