## Hospital Study Visit Overview

1. Obtain Informed Consent
2. Baseline Assessment (15 minutes)
  - a. Assess consciousness
    - i. Glasgow Coma Scale
    - ii. Mini Mental Status Exam
  - b. Demographic Questionnaire
  - c. Media Use Survey
  - d. Personal Health Questionnaire-8
  - e. Pre-Treatment Pain Questionnaire
  - f. Present Mood Questionnaire
3. Treatment Conditions
  - a. Film VR condition (30 minutes)
    - i. Samsung Gear VR information session
      1. Participants will receive information describing the Gear VR and instructed to fully engage with the VR video.
    - ii. Samsung Gear VR Fitting
      1. Gear VR will be adjusted to participant's head
    - iii. Watch 9 minute 360° 3D HD VVR film
    - iv. Administer Post-Treatment Assessments (5-10 minutes)
      1. Post-Treatment Pain Questionnaire
      2. Present Mood Questionnaire
      3. Presence Inventory
      4. Absorption Survey
      5. Attitudes Toward the Experience Survey
      6. Human Presence Survey
      7. Location Familiarity Survey
    - v. Wait 10 minutes
    - vi. Administer both the Follow-Up Pain Questionnaire & Present Mood Questionnaire (3-5 minutes)

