## Research Proposal

---

- b. Animated VR condition (30 minutes)
    - i. Samsung Gear VR information session
      1. Participants will receive information describing the Gear VR and instructed to fully engage with the VR video.
    - ii. Samsung Gear VR Fitting
      1. Gear VR will be adjusted to participant's head
    - iii. Watch 9-minute animated film
    - iv. Administer Post-Treatment Assessments (5-10 minutes)
      1. Post-Treatment Pain Questionnaire
      2. Present Mood Questionnaire
      3. Presence Inventory
      4. Absorption Survey
      5. Attitudes Toward the Experience Survey
      6. Human Presence Survey
      7. Location Familiarity Survey
    - v. Wait 10 minutes
    - vi. Administer both the Follow-Up Pain Questionnaire and Present Mood Questionnaire (3-5 minutes)
  - c. Waitlist condition
    - i. Participants will be directed to wait patiently for 9 minutes
    - ii. Administer both the Follow-Up Pain Questionnaire & Present Mood Questionnaire (3-5 minutes)
    - iii. Participants can choose to watch one of the two treatment VR videos for 9 minutes.
      1. Administer Post-Treatment Pain Questionnaire
4. Open Interview (3-5 minutes)
  5. One-week e-mail follow-up (10-15 minutes)
    - a. Follow-Up Pain Questionnaire
    - b. Present Mood Questionnaire
    - c. Participant Satisfaction Survey

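### Participants who cannot watch comfortably after headset fitting leave the whole study, so in-visit outcomes are lost from the two VR arms only

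*Protocol*

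**What the plan says.** Section 4, Treatment, describes headset fitting after consent and baseline. If adjustment does not help and "they cannot watch the video comfortably, they will be thanked for their time and their participation in the study will end", nothing further is scheduled for that person. Discomfort once viewing has begun is handled by a separate sentence, which says only that "if at any time they become uncomfortable or wish to stop using the Gear VR, they may do so at anytime"; it does not end study participation.

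The Hospital Study Visit Overview lists "Samsung Gear VR Fitting" under the film condition (3a) and again under the animated condition (3b). The waitlist condition (3c) has no such step: "Participants will be directed to wait patiently for 9 minutes", then the pain and mood forms, and only then an optional video. The Conditions text puts that offer later still: "After completion of the study visit, we will give those in the waitlist condition the option".

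Under Post-Treatment Assessments, once the 9 minutes of viewing or waiting are over, "participants in each condition will complete post-treatment assessments for 5-10 minutes", and "the Follow-Up Pain Questionnaire & Present Mood Questionnaire will be administered 10 minutes following the treatment". The one-week survey goes to participants, with no provision for anyone whose participation has been ended. The hypothesis at the end of section 3 is comparative on both sides: "We hypothesize that the film VR will show greater pain reductions and increased functioning relative to both the animated VR and the waitlist condition".

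**The concern.** A person assigned to VR who cannot use the headset comfortably is still a randomised person, and their pain after the session belongs to the comparison with waitlist. Under this rule their post-baseline pain and mood are not measured, whereas a waitlist patient with the same intolerance is measured as usual because no headset is tried before the waitlist forms. The loss follows allocation and occurs on one side only. The hypothesised comparison of film VR with waitlist then lacks outcomes for part of one arm, and that part is selected on tolerance of the intervention.

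The likely direction favours VR, since people who could not watch had no VR benefit. That is an inference, not something the protocol shows.

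There is also a safety side. The Post-Treatment Assessments text says nausea, dizziness, eyestrain and head pain are assessed to establish their incidence. People removed for discomfort never reach that form, so incidence may be understated. Adverse event recording may catch some of these events, but it is not that instrument.

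**Working it through.** **Does the rule end the study or only the session?** Two sentences in the same Treatment section differ. The fitting sentence ends participation in the study; the viewing sentence ends use of the device. Section 6d likewise lets participants stop the exposure without saying they leave. The literal reading of the fitting sentence stands.

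**Whom can it reach before the in-visit outcomes?**
- Film (3a) and animated (3b): fitting, viewing, then outcome forms. The rule can act before any outcome.
- Waitlist (3c): waiting, outcome forms, then optional viewing. The rule cannot act before the in-visit outcomes. If a waitlist patient fails fitting at the optional viewing, the one-week survey could still be lost, so the one-sidedness is strict only for the in-visit outcomes.

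**What is held on those removed?** Baseline forms are. Chart pain ratings may be, for those who sign the HIPAA form (Collecting Data from Medical Records), but nothing says this covers removed people, and chart ratings are not the study forms at the study times.

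**Size.** The protocol's own total reproduces: 3 × 67 = 201. It gives no rate of failed fitting. The figure of under 10% in section 6d concerns cyber sickness symptoms with older technology and bounds the fitting rate in neither direction. The shares below are therefore assumptions.

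Let q be the share of a VR arm removed.
- Removed per VR arm = 67q; across both = 134q.
- Suppose completers gain 1.0 point on the numerical rating scale (NRS) and those removed gain nothing but otherwise resemble the rest. The effect in all randomised is then (1 − q) × 1.0 + q × 0. This is a gap between two target groups.
- Suppose VR has no effect and those removed score k = 1 point above their whole arm's mean m. From m = (1 − q)c + q(m + k), the completer mean is c = m − qk/(1 − q), so completers look better than their whole arm by qk/(1 − q).

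| q (assumed) | Removed per VR arm | Removed, both VR arms | Effect in all randomised | Null-case shift |
|---|---|---|---|---|
| 2% | 1.34 | 2.68 | 0.98 | 0.020 |
| 5% | 3.35 | 6.70 | 0.95 | 0.053 |
| 10% | 6.70 | 13.40 | 0.90 | 0.111 |

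If the gap is instead measured between those removed and the completers, the shift is q × gap. At q = 10%, assumed gaps of 0.5 to 2 points give 0.05 to 0.20 points.

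Section 6a describes the 201 as people who complete everything, with over-recruitment for dropouts. On that reading each VR arm randomises 67/(1 − q), rounded up: 69, 71 or 75. That is 4, 8 or 16 randomised VR participants across both arms without outcomes, and none in waitlist by this rule. In effect they are replaced by people who tolerate the headset.

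The protocol gives no standard deviation, so no false-positive rate can be derived.

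**The case against.** The strongest counter-argument is that the arm restriction is inferred. The Treatment text speaks of participants being fitted after baseline without naming an arm, the Conditions text exempts the waitlist only from the VR exposure itself, and randomisation is never timed. If everyone were fitted, or fitted before allocation, the asymmetry would vanish. But the Overview is the step-by-step schedule; it puts fitting inside the assigned VR conditions and gives the waitlist none. That outweighs looser wording elsewhere, though the timing of randomisation remains a stated assumption.

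Second, an analysis of everyone randomised is still possible with a missing-data method. That is true, but it would rest on untestable assumptions about the very people the rule selects, and it cannot recreate the forms.

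Third, the effect may be slight. Section 6b already excludes people with certain hearing, sight or head-position problems, facial or head lesions, a seizure history, or unwillingness because of motion sickness. Film versus animated, the contrast that leads the stated aim, shares the headset and the fitting step. This stands, and it limits the severity.

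Fourth, the remedy has rough edges. Removed people would answer about the last 10 minutes, while those who watched answer about pain during VR. The two windows nearly coincide (10 minutes against 9), and the waitlist already uses the last-10-minutes form. The Overview lists only one controlled waitlist assessment, but the Post-Treatment Assessments text does not limit the 10-minute follow-up to the VR arms. Keeping to the schedule does mean waiting as well as form-filling, within a visit already planned at about 1 hour.

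**Conclusion.** The point holds. The fitting rule ends data collection, not just the VR session, and before the in-visit outcomes it can do so only in the film and animated arms. It should be fixed because the loss is built in, falls on one side of the VR versus waitlist comparison, and cannot be repaired at analysis.

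The bias is probably small and its size is unknown. For assumed removal of 2% to 10%, the illustrations give a 0.02 to 0.10 point difference between completers and all randomised when the completer effect is 1.0 point, and a null-case shift of 0.02 to 0.11 points when those removed score 1 point above their arm's mean. The conclusion rests on fitting following allocation, as the Overview's layout implies. The direction in favour of VR is inferred. Nothing here shows that a trial conclusion would change.

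**What to change.** Leave the rule for stopping the headset as it is. In the Treatment text, replace the closing words of the fitting sentence so that only the VR session ends. Add one line under 3a and 3b of the Overview for people who do not watch. Unless they withdraw, they:
- complete the Follow-Up Pain Questionnaire and the Present Mood Questionnaire when their arm's post-treatment forms fall due, which also matches the waitlist form after its 9-minute wait, and again at the 10-minute follow-up;
- complete the applicable Negative Effects items;
- receive the one-week survey;
- stay in their assigned arm, with removals reported by arm.

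The Post-Treatment Pain Questionnaire does not suit them, because it asks about pain during VR.

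The cost is two small text edits, a few minutes of questionnaires twice, and the waiting between them, inside the visit already planned. The estimated VR effect may come out slightly smaller.

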## Research Proposal

---

Participants in the standard animated video VR film condition will view the same content for the same duration as in the enhanced film condition, but the footage will be animated instead of photorealistic. Participants in the waitlist condition will be instructed to wait for 9 minutes.

### Post-Treatment Assessments

Following the 9 minutes of VR exposure or waiting, participants in each condition will complete post-treatment assessments for 5-10 minutes. These assessments will measure pain, presence, mood, negative effects of VR, absorption, human presence, participant's prior familiarity with the locations depicted in the VR video, and their attitude toward the VR session immediately after the treatment. Nausea, dizziness, eyestrain, and head pain is being assessed in an effort to identify the incidence of this component of simulator sickness sometimes associated with VR use (Kennedy et al., 1992). Following the Post-Treatment assessments, the Follow-Up Pain Questionnaire & Present Mood Questionnaire will be administered 10 minutes following the treatment. These follow-up assessments are in place in order to track the lasting pain reduction from the VR treatments.

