### 5. Measures

Assessments will be collected as outlined in the table below

Table. Assessment Schedule		Study Visit Before Treatment	Study Visit After Treatment	1-Week Follow-Up
Assessments				
Glasgow Coma Scale		X		
Abbreviated Mini Mental Status Exam		X		
Demographics Questionnaire		X		
Media Use Survey		X		
Personal Health Questionnaire-8		X		
Pre-Treatment Pain Questionnaire		X		
Present Mood Questionnaire		X	X	X
Post-Treatment Pain Questionnaire			X	
Presence Inventory			X	
Absorption Survey			X	
Attitudes Toward the Experience Survey			X	
Human Presence Survey			X	
Location Familiarity Survey			X	
Follow-Up Pain Questionnaire			X	X
Open Interview			X	
Patient Satisfaction Survey				X

- Glasgow Coma Scale (GCS) (Teasdale & Jennett, 1974)

The Glasgow Coma Scale (GCS) (Teasdale & Jennett, 1974) is a commonly used instrument in clinical practice and provides a structured method for assessment of the level of consciousness. The GCS has good reliability and well-established cross-sectional construct validity (Prasad, 1996).

- Mini Mental Status Exam (MMSE) (Folstein, Folstein, & McHugh, 1975)

The Mini Mental Status Exam (Folstein et al., 1975) is a questionnaire used extensively in clinical and research settings to measure cognitive impairment. We will be using an abbreviated version in combination with the GCS to assess for adequate consciousness for participation in the study.

- Demographics Questionnaire

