## Research Proposal

---

Participants will be asked to provide standard demographic information (i.e. age, gender, race/ethnicity, level of education, etc.). Participants will also be asked about hearing and visual impairment as well as their history of motion sickness.

- **Media Use Survey**

The Media Use Survey is a brief 4-question survey aimed to determine the participant's typical prior use of TV, online videos, and video games. The measure also asks about prior use of a virtual reality headset.

- **Personal Health Questionnaire-8 (PHQ-8)**

The Patient Health Questionnaire 8-Item (PHQ-8) is a brief self-report measure of major depressive disorder (Koneke, Spitzer, & Williams, 2001). The PHQ-8 is considered to be a valid measure of depression for population-based studies and clinical populations (Kroenke et al., 2009), with a cut off score of equal to or greater than 10 considered diagnostic for current depression. The PHQ-8 is derived from the PHQ-9 by removing the last question regarding suicidality.

- **Pre-Treatment Pain Questionnaire**

The Pre-Treatment Pain Questionnaire will be used to assess the participant's pain prior to receiving VR treatment. It is derived from the Brief Pain Inventory (BPI; Cleeland and Ryan, 1994; Cleeland et al., 1996) and contains Numerical Rating Scales (NRS) aimed at assessing the participant's pain intensity, pain quality, pain interference, and pain relief, as recommended by the IMMPACT recommendations for outcome measures in clinical pain trials (Dworkin et al., 2005). The NRS is one of the most common measures for assessing pain, and has been a validated outcome measure of pain intensity (Breivik, Björnsson, & Skovlund, 2000; Breivik et al., 2008). The NRS was also chosen because it could be administered orally if patients cannot use their hands to write or use the iPad.

- **Present Mood Questionnaire**

The Present Mood Questionnaire will be used to assess the participant's current mood. The survey uses a labeled (0-10) NRS to measure the extent that the participant feels sad, anxious, happy, and tranquil.

- **Post-Treatment Pain Questionnaire**

The Post-Treatment Questionnaire will be used to assess the participant's pain during and following the virtual reality treatment. The NRS pain assessment questions are identical to the Pre-Treatment Pain Questionnaire, except questions are altered to specify pain the participant experienced during the VR treatment.

- **Presence Inventory**

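### The simulator-sickness items are asked only after treatment and the protocol contradicts itself on whether the waitlist answers them, so the result may be a post-exposure prevalence rather than an incidence

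*Protocol*

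**What the plan says.** **Aim.** Section 4, Post-Treatment Assessments, gives the purpose of the symptom items: "Nausea, dizziness, eyestrain, and head pain is being assessed in an effort to identify the incidence of this component of simulator sickness".

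**Timing.** The same paragraph places them after the exposure or the wait: "Following the 9 minutes of VR exposure or waiting, participants in each condition will complete post-treatment assessments for 5-10 minutes". The battery it describes includes negative effects of VR. In Section 5 the Presence Inventory is the form said to cover Negative Effects. The schedule, introduced by "Assessments will be collected as outlined in the table below", marks it only in the after-treatment column and has no columns by arm.

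**Baseline.** The forms listed before treatment cover consciousness, demographics, media use, depression, pain and mood. The nearest item is in the Demographics Questionnaire: "Participants will also be asked about hearing and visual impairment as well as their history of motion sickness". That is history, not current state.

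**Waitlist, first version.** Section 4, Conditions: "Those randomized to the waitlist group will complete all study procedures except the VR exposure". With the Post-Treatment Assessments text, this means the waitlist gets the battery.

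**Waitlist, second version.** Hospital Study Visit Overview, item 3.c, lists one assessment step after the wait: "Administer both the Follow-Up Pain Questionnaire & Present Mood Questionnaire (3-5 minutes". It then says "Participants can choose to watch one of the two treatment VR videos for 9 minutes", followed only by the Post-Treatment Pain Questionnaire. The Presence Inventory is listed for the two VR arms alone.

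**The concern.** Incidence means new cases. To count them one needs each patient's state beforehand or, failing that, an unexposed group asked the same questions. The protocol provides no baseline answer, and whether it provides an unexposed group depends on which section staff follow. Staff at different hospitals could each follow the protocol and collect different data.

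Existing symptoms are plausible here. All participants are hospital patients with current pain. The eligibility criteria set aside minor headaches (with sprains and toothaches) as qualifying pain, and exclude lesions, rashes or open wounds of the face, head, neck or ears. They do not exclude other head pain, current nausea or current dizziness. A history of motion sickness excludes only patients who are also unwilling to watch.

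What is at stake is the tolerability figure. Which questions are put, when and to whom is data collection, so an analysis plan cannot later supply answers to items that were never asked.

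**Working it through.** **Step 1: the two versions side by side.**

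| Source | Waitlist asked the symptom items? | Baseline symptom items? | What the data allow |
|---|---|---|---|
| Conditions; Post-Treatment Assessments | Yes | No | VR versus waitlist contrast, no within-patient change |
| Visit Overview, item 3.c | No | No | Post-exposure readings in the VR arms only |

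The assessment schedule cannot decide between them because it does not separate the arms. The protocol never says outright that the four symptoms are the Presence Inventory's Negative Effects items. That is an inference, but the stated timing is after treatment whichever form carries them.

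**Step 2: how far prevalence can depart from incidence.** The protocol states no figure to reproduce beyond the arm sizes (3 × 67 = 201, consistent). The rest is illustration. Let b be the share of patients with a symptom already, and v the share of symptom-free patients in whom VR induces one. The documents do not give b, so 0 to 30% is an assumption. The values 5% and 10% for v are also assumed. They are chosen around the statement under Risks that fewer than 10% report such symptoms with older technology. Worsening is not modelled.

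- Post-exposure reading = b + (1 − b)v
- New onset = (1 − b)v
- Excess of the reading over new onset = b

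| b | Reading, v = 5% | New onset, v = 5% | Reading, v = 10% | New onset, v = 10% |
|---|---|---|---|---|
| 0% | 5.0% | 5.0% | 10.0% | 10.0% |
| 10% | 14.5% | 4.5% | 19.0% | 9.0% |
| 20% | 24.0% | 4.0% | 28.0% | 8.0% |
| 30% | 33.5% | 3.5% | 37.0% | 7.0% |

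At b = 0 there is no distortion. A background of 10% with no VR effect (v = 0) reads 10%, the same as a true 10% incidence with no background. For scale, 13 of 134 VR patients (9.7%) has an exact 95% interval of 5.3 to 16.0%, so backgrounds in the upper part of the assumed range would outweigh sampling error.

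**Step 3: what a waitlist answer would add.** For 134 VR against 67 waitlist patients, with p the VR reading, the 95% half-width is 1.96 × √[p(1 − p)/134 + b(1 − b)/67].

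- v = 10%, b = 10, 20, 30%: ±9.8, 12.2, 13.7 points, against expected differences of 9, 8, 7 points.
- v = 5%, same b: ±9.3, 12.0, 13.6 points, against 4.5, 4.0, 3.5 points.

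The contrast is worth having but can only be descriptive.

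**Step 4: what baseline items would add to film versus animated.** With 67 per arm, assumed v of 5% and 10%, and b = 10, 20, 30%, the differences are 4.5, 4.0 and 3.5 points. The half-width is 12.6, 14.8 and 16.2 points on post-treatment readings, and 8.5, 8.0 and 7.5 points on new symptoms. Precision improves, but neither version excludes zero.

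**The case against.** **The wording may already solve it.** The battery is described as negative effects of VR, and the Post-Treatment Pain Questionnaire repeats the earlier items "except questions are altered to specify pain the participant experienced during the VR treatment". If the symptom items are tied to the session in the same way, existing symptoms are largely screened out. This stands as a condition on the point, because the wording is not shown. It does not settle whether the waitlist is asked.

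**New onset is recorded elsewhere.** The adverse-event section records complaints that begin or worsen after consent, with times and relationship to the intervention, and is not limited by arm. Diagnoses and progress notes are also available for patients who sign the HIPAA authorization. A reader might infer that no information on new symptoms will exist. The documents do not support that. The mitigation is partial, however, since adverse-event recording is not the set of four items to which the protocol attaches the incidence aim.

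**There is no benchmark.** A reader might infer that the figure will be inflated past a planned 10% threshold. The documents do not support that either. The figure under Risks describes what participants report with older technology, covers a wider symptom list, may itself be a post-exposure rate, and no comparison against it is planned. It is an approximate reference only.

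**The gain is modest.** The intervals above show little inferential return, and tolerability is not part of the stated hypothesis. This is fair, and it limits the point to a cheap improvement.

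**Conclusion.** The contradiction over the waitlist and the absence of baseline symptom items both rest on the text and need no assumption. The consequence is conditional. If the visit overview is followed, and unless the items are worded as caused by the session, the protocol will yield a post-exposure symptom prevalence without a baseline or an unexposed control. If the Conditions text is followed, there is an unexposed control but still no baseline.

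The size of the distortion equals the background prevalence, which is unknown: zero at no background, and up to 30 points at the top of the assumed range.

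A reader might also infer that the trial's main comparisons are compromised. For this point they are not. The pain hypothesis does not use these items, and film versus animated remains a valid randomised comparison, although two exposed arms cannot show how much VR itself adds. The point is a contradiction to reconcile plus an inexpensive improvement in data collection.

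**What to change.** 1. Reconcile the Conditions, Post-Treatment Assessments, Hospital Study Visit Overview and assessment-schedule text so that the waitlist answers the four symptom items after the wait and before any optional VR.
2. Ask the same four items at baseline, worded as current symptoms so that all three arms can answer them.
3. Report new or worsened symptoms by arm, with the waitlist contrast descriptive.

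If the baseline items are declined, still resolve the contradiction and call the result post-exposure symptom prevalence.

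The cost is four questions per patient at baseline, four more for the 67 waitlist patients if the visit overview is current practice, and edits to the forms and schedule. The main downside is that asking beforehand may prime symptom reports, and the waitlist would not remove priming that acts together with VR.
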